4.3.4. Overall Response Rate (ORR)

4.3.4.1. **Definition**

ORR is defined as the proportion of subjects who achieve a partial response or better (i.e., PR, VGPR, CR or sCR) based on the computerized algorithm, according to IMWG response criteria, during or after the study treatment.

4.3.4.2. Analysis Methods

Similar statistical methods will be applied as described in Section 4.3.1.2 for CR or better rate analysis.

4.3.5. Overall Survival

4.3.5.1. **Definition**

Overall survival (OS) is measured from the date of randomization to the date of death due to any cause. Subjects who are lost to follow-up will be censored at the time of lost to follow-up. Subjects who are still alive at the clinical cut-off date for the analysis will be censored at the last known alive date. The date of last known alive will be determined by the maximum collection/assessment date from among selected data domains within the clinical database.

4.3.5.2. Analysis Methods

OS, including 12, 24 and 36-months survival rate, will be analyzed for the ITT population. The Kaplan-Meier method will be used to estimate the distribution of OS for each treatment group. Median OS with 95% CI will be provided. In addition, the number and percentage of subjects who had died or were censored will be reported. Additionally, the survival rate with 95% CI at 12, 24 and 36-months will be estimated using Kaplan-Meier method for each treatment group.

Due to the expected small number of death events at the second interim analysis, the distribution of OS for the 2 treatment groups will be compared based on an un-stratified log-rank test. A p-value from an un-stratified log-rank test will be reported. Hazard ratio and its 95% confidence interval will be estimated based on an un-stratified Cox's regression model with treatment as the sole explanatory variable.

In addition, a summary of reasons for censoring of overall survival will be provided.

If the null hypothesis of OS is not rejected at the second interim analysis, for OS at the primary PFS analysis when 360 PFS events observed, the alpha to be spent will be determined by a linear alpha spending function based on the observed number of deaths at that time, i.e., the cumulative alpha to be spent will be the total alpha (0.05) multiplied by the proportion of the observed number of deaths out of the total planned number of deaths (330, expected at time of the final OS). See Section 4.1.1 for more details on alpha spending and type I error control.

4.3.6. Time to Disease Progression (TTP)

4.3.6.1. **Definition**

TTP is defined as the time between the date of randomization and the date of first documented evidence of confirmed PD, as defined in the IMWG response criteria, or death due to PD, whichever occurs first. Subjects who start subsequent antimyeloma therapies for multiple myeloma without disease progression will be censored at the last disease assessment before the start of subsequent therapies. Subjects who withdraw consent to study or are lost to follow-up or die without disease progression will be censored at the last disease assessment. Subjects who have not progressed at the cutoff date for analysis will be censored at the last disease assessment. Subjects without any post-baseline disease assessment will be censored at the randomization.

Determination of dates of TTP event and dates for censoring is summarized in Table 4 as follows.

Table 4: TTP Event and Censoring Method

Situation	Date of Progression or Censoring	Outcome
Disease progression prior to start of subsequent anticancer therapy	Earliest date that indicates disease progression	TTP event
Death due to disease progression prior to start of subsequent anticancer therapy	Date of death	TTP event
No post-baseline disease assessment	Randomization	Censored
Other (e.g., withdrawal of consent to study participation, lost to follow-up, start of subsequent anticancer therapy etc.)	Date of last disease assessment prior to subsequent anticancer treatment	Censored

4.3.6.2. Analysis Methods

Similar statistical methods will be applied as described in Section 4.2.2for PFS analysis, including descriptive and comparison of the distribution of overall TTP.

4.3.7. Progression-free Survival on Next Line of Therapy (PFS2)

4.3.7.1. **Definition**

Progression-free survival on next line of therapy (PFS2) is defined as the time from randomization to progression on next line of therapy or death, whichever comes first. Any deaths are considered as PFS2 events. Subjects who start next line of therapy without disease progression on study treatment will be censored at the last disease assessment before starting next line of therapy. For subjects who start next line of therapy after progression on study treatment, are still alive and not yet progress on next line of therapy, they will be censored on the last date of follow-up. Subjects without any post-baseline follow-up will be censored at the randomization.

Determination of dates of PFS2 event and dates for censoring is summarized in Table 5 as follows.

Table 5: PFS2 Event and Censoring Method

andomization	G 1
and on East on	Censored
ate of last disease assessment prior to start of 1st ne on next therapy	Censored
finimum of earliest date that indicates rogression on the 1 st line of next therapy and date	DEG2
	PFS2 event
	Censored
at iii o	e of last disease assessment prior to start of 1st on next therapy nimum of earliest date that indicates

4.3.7.2. Analysis Methods

Similar statistical methods will be applied as described in Section 4.2.2 for PFS analysis.

4.3.8. sCR Rate

4.3.8.1. **Definition**

sCR rate is defined as the proportion of subjects with a response of sCR based on the computerized algorithm, according to IMWG response criteria, during or after the study treatment

4.3.8.2. Analysis Methods

Similar statistical methods will be applied as described in Section 4.3.3.2 for CR or better rate analysis.

4.3.9. Time to Subsequent Antimyeloma Treatment

4.3.9.1. Definition

Time to subsequent antimyeloma treatment is defined as the time from randomization to the start of subsequent antimyeloma treatment. Death due to PD without start of subsequent

therapy will be considered as event. Subjects who withdrew consent to study or are lost to follow, or die due to causes other than disease progression will be censored at the date of death or the last date known to be alive.

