9.1.4. Follow-up Phase

The Follow-up Phase will begin once a subject discontinues all study treatments. Subjects who discontinue study treatment before disease progression must continue to have disease evaluations. Ideally, the timing of disease evaluations should follow the Time and Events Schedule until confirmed PD (see Section 8.4, Subsequent Therapies), death, the start of a new anti-myeloma therapy, withdrawal of consent, lost to follow-up, or the end of the study. After disease progression is documented, subsequent anti-myeloma therapy, PFS2 (per investigator judgment), second primary malignancies and survival status will be obtained at least every 16 weeks ±2 weeks until the start of the long-term survival follow-up. Every 16-week follow-up contacts, as well as Week 8 and Week 16 post-PD ECOG and ePRO assessments, should be scheduled from the date of confirmed progression (ie, the date of the confirmatory laboratory assessment, not the date of confirmation by the sponsor). In subjects for whom disease progression will not be documented (eg, received subsequent anti-myeloma treatment or refused disease evaluations, but agreed to follow-up contacts), the every 16-week follow-up should be scheduled from the date of the End-of-Treatment Visit.

For Follow-up Phase procedures during long-term survival follow-up, please see Attachment 11. If the information is obtained via telephone contact, written documentation of the communication must be available for review in the source documents. If the subject has died, the date and cause of death will be collected and documented in the eCRF.

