16.2.3. Informed Consent

Each subject (or a legally acceptable representative) must give written consent according to local requirements after the nature of the study has been fully explained. The ICF(s) must be signed before performance of any study-related activity. The ICF(s) that is/are used must be approved by both the sponsor and by the reviewing IEC/IRB and be in a language that the subject can read and understand. The informed consent should be in accordance with principles that originated in the Declaration of Helsinki, current ICH and GCP guidelines, applicable regulatory requirements, and sponsor policy.

Before enrollment in the study, the investigator or an authorized member of the study-site personnel must explain to potential subjects or their legally acceptable representatives the aims, methods, reasonably anticipated benefits, and potential hazards of the study, and any discomfort

participation in the study may entail. Subjects will be informed that their participation is voluntary and that they may withdraw consent to participate at any time. They will be informed that choosing not to participate will not affect the care the subject will receive for the treatment of his or her disease. Subjects will be told that alternative treatments are available if they refuse to take part and that such refusal will not prejudice future treatment. Finally, they will be told that the investigator will maintain a subject identification register for the purposes of long-term follow up if needed and that their records may be accessed by health authorities and authorized sponsor personnel without violating the confidentiality of the subject, to the extent permitted by the applicable law(s) or regulations. By signing the ICF the subject or legally acceptable representative is authorizing such access, including permission to obtain information about his or her survival status, and agrees to allow his or her study physician to recontact the subject for the purpose of obtaining consent for additional safety evaluations, if needed, and subsequent disease-related treatments, or to obtain information about his or her survival status.

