For subjects continuing study treatment during the long-term survival follow-up, serious adverse events that occur while the subject is receiving study drug or are within 30 days after the last dose of study drug, will be collected and reported to the sponsor's global medical safety database via serious adverse event reporting process as indicated by Sponsor or designee (see Section 12.3.2). Serious adverse events that occur between 30 days after the last dose of the study drug and the end of study should be reported using the same process if considered by the investigator to be related to study drug. All serious adverse events should also be documented in the subject file/source notes.

Pregnancy reporting should continue as described in Section 12.3.4. The pregnancy should be documented in the subject file/source notes.

During long-term survival follow-up, reporting of anticipated events (Attachment 10) is no longer performed.

Patient Reported Outcomes

For subjects continuing study treatment during the long-term survival follow-up, no PRO data collection will occur.

Sample Collection and Handling

For subjects continuing study treatment during the long-term survival follow-up, there will be no PK, immunogenicity, or biomarker (MRD) assessments during this treatment period. Any sample collection or test for safety or disease evaluation should comply with local institution practice and be documented in the subject files/source notes.

Case Report Form Completion

The clinical database will remain partially open during the long-term survival follow-up. For all subjects on study, whether continuing study treatment or those in survival follow-up, CRF pages to be completed are:

- subsequent therapies
- survival follow-up
- death information
- end of treatment disposition
- end of study disposition

For survival follow up, the information can be obtained via telephone contact, medical records indicating the subject visited the hospital (laboratory, consult for other specialty), public records for deaths, etc.

Follow-up Procedures

For subjects who discontinue treatment during the long-term survival follow-up and the subjects who were in follow-up at the time of final CSR analysis, end of treatment procedures (Section 9.1.4) are not applicable, except for HBV DNA monitoring in accordance with the local label. These monitoring data should be documented in files/source notes but not entered in the CRF.

Source Documentation

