4.2.1. Definition

PFS is defined as the duration from the date of randomization to either progressive disease, according to the IMWG response criteria, or death, whichever occurs first. Subjects who start subsequent antimyeloma therapies for multiple myeloma without disease progression will be censored at the last disease assessment before the start of subsequent therapies. Subjects who withdrew consent from the study before disease progression will be censored at the last disease assessment before withdrawal of consent to study. Subjects who are lost to follow-up will be censored at the last disease assessment before subjects are lost to follow-up. Subjects who have not progressed and are still alive at the cutoff date for analysis will be censored at the last disease assessment. Subjects without any post-baseline disease assessment will be censored at the randomization.

Determination of dates of PFS event and dates for censoring is summarized in Table 2 as follows.

Table 2: PFS Event and Censoring Method

Situation	Date of Progression or Censoring	Outcome
Disease progression prior to start of	Earliest date that indicates disease progression	PFS event
subsequent antimyeloma therapy		
Death without subsequent antimyeloma	Date of death	PFS event
therapy		
No post-baseline disease assessment	Randomization	Censored
Other (e.g., withdrawal of consent to study	Date of last disease assessment prior to	Censored
participation, lost to follow-up, start of subsequent	withdrawal of consent to study participation, lost to	
antimyeloma therapy etc.)	follow-up, or subsequent antimyeloma treatment	
/	- · · ·	

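### Time to subsequent therapy censors withdrawn and lost subjects at a survival date, so any time after therapy follow-up stops counts as therapy-free

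*SAP*

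**What the plan says.** SAP 4.3.9.1 measures this endpoint from randomization to the start of next therapy and counts death due to PD without next therapy as an event. Subjects who withdraw consent, are lost, or die of other causes "will be censored at the date of death or the last date known to be alive".

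The last-known-alive date is defined under overall survival, in SAP 4.3.5.1: "The date of last known alive will be determined by the maximum collection/assessment date from among selected data domains within the clinical database". Nothing there links the date to knowledge of subsequent therapy.

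Other endpoints in the SAP stop at their own follow-up. For PFS (4.2.1), "Subjects who withdrew consent from the study before disease progression will be censored at the last disease assessment before withdrawal of consent to study", with a parallel rule for loss. TTP (4.3.6.1) also stops at the last disease assessment. PFS2 (4.3.7.1) stops at the last date of follow-up for subjects alive and not progressed on next therapy.

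On data collection, Protocol 9.1.4 says that after progression "subsequent anti-myeloma therapy, PFS2 (per investigator judgment), second primary malignancies and survival status will be obtained at least every 16 weeks". The consent described in Protocol 16.2.3 gives access to records, "including permission to obtain information about his or her survival status". In long-term survival follow-up (Protocol Attachment 11), sources for survival include "medical records indicating the subject visited the hospital (laboratory, consult for other specialty), public records for deaths". Protocol 9.2.2 defines time to next treatment but gives no censoring rule, so SAP 4.3.9.1 is the only rule for this endpoint.

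**The concern.** A subject should stay at risk only while the event could be recorded. Here the event is the start of a therapy, but for withdrawn and lost subjects the end of the risk period is set by survival information. A death record or a hospital visit for another specialty can show that someone was alive or dead on a date without showing whether myeloma therapy had begun. Time between the last therapy information and that date adds to the denominator and cannot add an event.

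The Kaplan-Meier median is then too long. If one arm has more withdrawals, its curve is lifted more, and the stratified log-rank test and Cox hazard ratio planned in SAP 4.3.9.2 shift in that arm's favor. This is a named secondary endpoint of an open-label trial.

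**Working it through.** **Inputs from the documents.** Annual dropout 5%, not split by arm (Protocol 11.2, SAP 1.3). Accrual 21 months plus 24 months of follow-up, 1:1 allocation, PFS hazard ratio 0.75, control median PFS 24 months, two-sided alpha 0.05, 80% power. Follow-up contacts at least every 16 weeks after PD (Protocol 9.1.4).

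**Assumptions.** The documents give no figures for time to next therapy. I take exponential times with true medians of 24 and 36 months. The gap between last therapy information and last-known-alive date is set at 0, 16 weeks (112/30.4 = 3.7 months), 12 months, or up to cut-off as the extreme. A 10% annual dropout in one arm illustrates imbalance.

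**Step 1: reproduce the plan's own figure.** The only stated calculation that uses dropout is the PFS design.
- Events (Schoenfeld): 4 × (1.960 + 0.842)² / (ln 0.75)² = 4 × 7.849 / 0.0828 ≈ 380. Freedman's formula gives 385. The plan states 390, which gives 81.1% power.
- Dropout hazard: δ = −ln(0.95)/12 = 0.00427 per month. The average event probability is 0.539, so N = 390/0.539 ≈ 724, against about 730 stated.

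The design reproduces, so the same accrual, follow-up and dropout model is used below.

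**Step 2: effect on the median.** Let λ = ln 2/median be the true hazard and g the gap. Once t exceeds g, the ratio of subjects wrongly kept at risk to those truly under observation is

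r = δ/(λ + δ) × (exp[(λ + δ)g] − 1),

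and the estimated hazard is λ/(1 + r). For median 24 (λ = 0.0289):
- g = 3.7: r = 0.129 × (e^0.123 − 1) = 0.017
- g = 12: r = 0.129 × (e^0.398 − 1) = 0.063

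Before t reaches g the ratio is still building up, so the median rises by slightly less than the factor 1 + r. Integrating the hazard gives 24.4 and 25.1 months. A simulation with 1,000,000 subjects per arm agrees to within 0.1 month:

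| Gap | True median 24 | True median 36 |
|---|---|---|
| 0 | 24.0 | 36.0 |
| 16 weeks | 24.3 (+0.3) | 36.6 (+0.6) |
| 12 months | 25.1 (+1.1) | 37.8 (+1.8) |
| To cut-off | 25.8 (+1.8) | 40.1 (+4.1) |

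The gap-0 row is the proposed rule, and it recovers the truth. About 9% to 10% of subjects are lost before an event or cut-off in these scenarios.

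**Step 3: effect on the hazard ratio** (true value 0.75; control median 24; ratio of event rates, which is appropriate for exponential times).

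| Annual dropout, Rd / DRd | 16 weeks | 12 months | To cut-off |
|---|---|---|---|
| 5% / 5% | 0.750 | 0.752 | 0.754 |
| 10% / 5% | 0.76 | 0.79 | 0.82 |
| 5% / 10% | 0.74 | 0.72 | 0.69 |

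Equal dropout leaves the ratio where it was. Unequal dropout moves it in either direction, depending on which arm loses more subjects.

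**The case against.** The strongest reply is that the gap will usually be small.
- The Follow-up Phase ends at withdrawal of consent or loss (Protocol 3.1), and Protocol 10.3 removes such subjects from the study, so no survival contact is scheduled afterwards.
- Protocol 9.1.4, 9.1.5 and 9.1.7 collect therapy and survival together, so a lost subject's last alive contact is normally also the last therapy contact.
- Attachment 11 applies only after the final CSR analysis. It came with Amendment 9 in 2021, whereas SAP version 2.0 dates from October 2018. It also requires the subsequent-therapies page for every subject on study.
- The consent sentence in Protocol 16.2.3 goes on to mention recontact and later disease-related treatment, so it is not confined to vital status.
- PFS2 is a closer comparator than PFS, because start of therapy is learned by contact and not by scheduled disease assessment.

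All of this stands as to size. It does not remove the rule. The alive date is a maximum over data domains, and any survival-only update moves it past the last therapy information.

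Two further points also stand. Censoring a non-PD death under active follow-up at the date of death is proper; the remaining question there is competing risk. A PD death learned after withdrawal counts as an event, which partly offsets the excess.

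A reader might infer that the endpoint is overstated in every case, or that the treatment comparison is biased. The documents support neither. The excess needs a gap, and no withdrawal figures by arm are given.

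**Conclusion.** The point holds in a conditional form. SAP 4.3.9.1 ends the risk period of withdrawn and lost subjects at a date not tied to ascertainment of next therapy. Where vital status is learned later, the median is too long: about 0.3 to 0.6 months for a 16-week gap and about 1 to 2 months for a 12-month gap. Only when vital status is known to cut-off for all those lost does it reach about 2 to 4 months. These figures rest on the plan's 5% annual dropout and on assumed exponential times with medians of 24 to 36 months.

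The hazard ratio is essentially unaffected under equal dropout. A shift between arms is a possibility to guard against, not a finding. The endpoint is not in the hierarchy of SAP 4.1.1, so no alpha-controlled test is touched. This is a modest correction, worth making because it is cheap.

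**What to change.** Replace the censoring sentence in SAP 4.3.9.1 as follows.
- Subjects who withdrew or were lost without a recorded next therapy: censor at the last study visit or follow-up contact on or before withdrawal or loss, and no later than the clinical cut-off. Apply this also when a later death that is not an event is learned from another source. Using the last visit or contact keeps the date defined for subjects without PD, whose scheduled therapy follow-up starts only after PD.
- Non-PD deaths under active follow-up: keep censoring at the date of death.
- Overall survival: keep the last-known-alive date.
- Report the current rule as a sensitivity analysis, with withdrawals and losses by arm.

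The same edit can name the censoring date for subjects still followed and therapy-free at cut-off, which 4.3.9.1 does not state.

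The cost is a short SAP edit and one date derived from existing visit and follow-up data. The downside is slightly shorter follow-up for this endpoint. Where there is no gap, the result does not change.

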4.3.9.2. Analysis Methods

The Kaplan-Meier method will be used to estimate the distribution of time to subsequent antimyeloma treatment for the ITT population. Median time to subsequent antimyeloma treatment with 95% CI will be tabulated for each treatment group. In addition, a Kaplan-Meier curve for time to subsequent antimyeloma treatment will be plotted. The hazards ratio and its 95% CI will be obtained through a stratified Cox's regression model with treatment as the sole explanatory variable. Treatment comparison will be made via a stratified log-rank test.

4.3.10. Time to Response

4.3.10.1. Definition

Time to response (i.e., time to first response) is defined as the time between the date of randomization and the first efficacy evaluation that the subject has met all criteria for PR or better based on the computerized algorithm for patients who had PR or better as their best response.

